effect using linear contrasts from a logistic regression model. Specifically, we will use two separate Wald tests based on logistic regression, with stratification by recruitment site and baseline risk group (medium, high). Let Y_{ij} denote the primary outcome status (0=not chronic; 1=chronic) for subject i in site j , and let $Site(2)$ be an indicator variable used to code the two recruitment sites. All analyses will adjust for site and the baseline risk status represented by $RiskGroup$ (0=medium risk; 1=high risk). In order to code the treatment groups we use the variables SMT (0=no; 1=spinal manipulation therapy), and SSM (0=no; 1=supported self-management). Given interruption by COVID-19 and period of restricted randomization we will adjust for this using the variables $Period(k)$ which will be an indicator for: 1=UG3 and UH3 through March 2020; 2=calendar period of restricted randomization; and 3=calendar period of resumed full factorial randomization. Regression models for the outcome are used to structure the probability of chronic back pain as follows:

$$Additive\ Model \quad \text{logit}[P(Y_{ij} = 1 | X_{ij})] = \beta_0 + \beta_1 \cdot Site(2)_j + \beta_2 \cdot RiskGroup_{ij} + \beta_3 \cdot SMT_{ij} + \beta_4 \cdot SSM_{ij} + \beta_5 \cdot Period(2)_{ij} + \beta_6 \cdot Period(3)_{ij}$$

$$Full\ Model \quad \text{logit}[P(Y_{ij} = 1)] = \beta_0 + \beta_1 \cdot Site(2)_j + \beta_2 \cdot RiskGroup_{ij} + \beta_3 \cdot SMT_{ij} + \beta_4 \cdot SSM_{ij} + \beta_5 \cdot SSM_{ij} \cdot SMT_{ij} + \beta_6 \cdot Period(2)_{ij} + \beta_7 \cdot Period(3)_{ij}$$

Our original application proposed using an additive model to generate a single summary parameter that describes the SMT effect (β_3) and the independent SSM effect (β_4). However, the additive model uses an assumption that the effect of one intervention is independent of whether the other intervention is delivered. Such an assumption is not necessary, and a full model can be used to make inference on a single linear contrast for each treatment that represents an average treatment effect.

The “Full Model” can then be used to derive an overall or average effect of SMT, and an overall or average effect of SSM. Specifically, focusing on the effect of SMT the model yields:

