In 2021, the NIH statistician overseeing the trial raised the question of the adequacy of the planned adjustment for multiplicity given the trial's three main effectiveness objectives and accompanying four co-primary outcome measures. In response to this concern, the lead investigators recommended the recovery objective be changed to a key secondary outcome. Early in the conduct of the trial it was decided and approved as a protocol change to include patients that had an acute aggravation of ongoing LBP, if the ongoing pain was not rated as severe in the month prior to the aggravation. This protocol change substantially lowers the proportion of patients that can be expected to recover according to our criteria (pain severity = 0 and RMD score ≤ 2). Given this change, the recovery outcome was less appropriate as a primary effectiveness objective and demoting it to a secondary outcome mitigates the concern of cross-objective multiplicity control.

In 2022 NCCIH and the DSMB approved that the recovery effectiveness objective, formally one of the 3 primary effectiveness objectives, will be designated as a key secondary outcome.

[figure not shown]
Recovery Effectiveness Hypothesis: SMT alone will increase the rate of recovery by 5.5-7.5% or more from a baseline MC rate of 5%-15%. Similarly, SSM alone will increase the rate of recovery from 5.5-7.5%, and the combination of SMT+SSM will lead to an additive net increase in the recovery rate.

Recovery outcome definition: For a patient to be classified as recovered at the 6 month or 1 year assessment they must endorse both an NRS of 0, and an RMDQ of ≤ 2 .¹⁵² To evaluate recovery we will consider the 6-month status first and use the 1-year status second.

Recovery Analysis: The primary analysis will be two parallel tests of the average effects of SMT and SSM in a full logistic regression model for the primary outcome (recovery at 6 months). The primary analysis for recovery will use pre-specified linear contrasts for hypothesis testing regarding overall or average effects.

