Power and Sample Size for the Recovery Outcome: In order to determine the necessary sample size for effectiveness evaluation we need to formulate assumptions for the primary outcome rate in the treatment and control groups. [name] et al.¹¹ compared SMT plus Home Exercise with Advice (HEA) to HEA alone among subacute and chronic patients and find complete recovery from leg pain in 20% of SMT+HEA versus 5% of HEA at 12 weeks, and 23% versus 12.5% respectively at one year (RR=1.84) providing evidence that relative risks in the range of 1.5-2.0 are plausible. The recovery rate at 6 months was estimated based on studies by Kamper et al.¹⁵² and members of our investigative team,¹⁵³ which used the same strict definition for recovery. Kamper et al.¹⁵² summarize recovery rates and criteria based on both NRS and RMDQ from four studies with acute and subacute subjects. Recovery rates range from 7% to 12%. A recent study by [name] et al.¹⁵³ reported a 5% recovery rate within a mixed population of sub-acute and

chronic patients with increased risk for cLBP. Given the potential uncertainty in the recovery rate for the MC group, we varied the expected recovery rate from 5-15% and determined the magnitude of treatment effects for which we have $\geq 80\%$ power.

For simulations we considered crude analysis while our formal analysis will additionally adjust for site and baseline risk yielding improved power since these are variables that only predict outcome and are not related to treatment group. For each scenario we simulated 5,000 data sets and empirically calculated power as the percentage of replicates in which the null hypothesis was rejected.

Figure 9.2 shows the power to test each intervention marginally. We see that we have >80% power to detect a relative risk of 1.75 associated with either SMT or SSM if the UMC recovery rate is 10%. If the UMC recovery rate is 5% then we have power to detect a 5.5% risk difference (RR=2.1), while if the UMC recovery rate is 15% then we have power to detect an 8.3% risk difference (RR=1.55). These effects are also medium in size and considered clinically important by Cochrane's Back Review Group.¹⁴⁸

Primary Effectiveness Outcome # 2 and 3: Determine the effectiveness of SMT, SSM, and the combination of SMT+SSM relative to medical care (MC) in achieving improvements in average pain intensity and back-specific functioning cumulative through 1 year based on monthly measures of RMDQ and weekly Pain NRS scores.

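### The recovery models, as far as the plan specifies them, leave out baseline NRS and RMDQ; adding these already-collected covariates would bring a small gain in power of uncertain size

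*Combined protocol and SAP*

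**What the plan says.** All references are to the combined protocol and SAP, section 9 unless stated.

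- **Endpoint.** To count as recovered at 6 months or 1 year, "they must endorse both an NRS of 0, and an RMDQ of ≤ 2". The 6-month status comes first and the 1-year status second. Recovery was formerly primary and "will be designated as a key secondary outcome".
- **Model.** Under Recovery Analysis: "The primary analysis will be two parallel tests of the average effects of SMT and SSM in a full logistic regression model". No equation or covariate list follows.
- **Where the covariates can be read from.** The only Full Model in logistic form is under Secondary Chronicity outcome Analysis, described as "with stratification by recruitment site and baseline risk group (medium, high"). That text adds "All analyses will adjust for site and the baseline risk status represented by" a risk-group indicator, and for period: "Given interruption by COVID-19 and period of restricted randomization we will adjust for this using the variables" for the three calendar periods. The August 2020 modification also extends period adjustment to every analysis.
- **Recovery power text.** "For simulations we considered crude analysis while our formal analysis will additionally adjust for site and baseline risk yielding improved power". The reason given is that such variables predict outcome but are unrelated to treatment group.
- **Contrast with pain and disability.** The Primary Analysis for outcomes 2 and 3 adds the baseline value of the outcome to the four-group linear model. No sentence does this for recovery.
- **Availability.** Section 6.2.2 collects both NRS and RMDQ at baseline.

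**The concern.** Recovery is a threshold on two scales, and each participant's starting position on both is known before randomisation. A two-level STarT Back group is at best a coarse substitute for those scores. If they predict recovery, adjusting for them raises the power of a randomised comparison in a logistic model and removes chance baseline imbalance on the scales that define the endpoint.

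The plan already accepts that argument when it justifies adjusting for site and risk. Recovery is also an endpoint where modest gains could be useful: the assumed rate under medical care is only 5 to 15%, and the plan says that admitting aggravations of ongoing pain lowers the proportion who can be expected to recover. At stake is a few points of power at most, on a key secondary outcome.

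**Working it through.** **1. Reproduce the plan's figure.** The plan states more than 80% power, on a crude analysis, for 10% recovery under medical care (MC) and a relative risk of 1.75.

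Inputs:
- Recovery rates: MC 10%; SMT alone and SSM alone 10% × 1.75 = 17.5%; combined 10 + 2 × 7.5 = 25% (the recovery hypothesis is additive).
- Sample: 1000 × 90% = 900. This is stated for LBP Impact and chronicity and taken over here. The 300/300/200/200 allocation becomes MC 270, SSM 270, SMT 180, SMT+SSM 180.
- Two-sided alpha 0.05 (0.05 is stated for the chronicity tests; two-sided is assumed).

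Average SMT effect, β3 + ½β5:
- Logits: −2.197 (10%), −1.551 (17.5%), −1.099 (25%).
- Effect = ½[(−1.551 + 2.197) + (−1.099 + 1.551)] = 0.549.
- Variance = ¼ Σ 1/[n p(1−p)] = ¼(0.0412 + 0.0257 + 0.0385 + 0.0296) = 0.0337, so SE = 0.184.
- Power = Φ(0.549/0.184 − 1.96) = Φ(1.03) = 84.9%. The average SSM effect gives the same value.

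Pooled margins give 83.2% (SMT) and 85.5% (SSM). A 5,000-replicate simulation of the Wald contrast gives 84.2% and 86.4%. The stated figure reproduces. In the plan's other two scenarios, simulated SMT/SSM power is 78.4/80.9% (5%, RR 2.1) and 82.3/83.6% (15%, RR 1.55), consistent with about 80%.

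**2. Separate the effect of period.** No SMT patients were randomised in the restricted period. With an assumed 90 MC and 90 SSM participants in it (270 − 180), the period-adjusted SMT contrast rests essentially on 180 per arm:
- Variance = ¼(0.0617 + 0.0385 + 0.0385 + 0.0296) = 0.0421, so SE = 0.205.
- Power = Φ(0.549/0.205 − 1.96) = Φ(0.72) = about 76%.

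The simulations of the Full Model with site, risk group and period start at about 77 to 78% for SMT. That starting level is due mainly to period adjustment, not to the missing baseline scores.

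**3. Add baseline NRS and RMDQ.** The same simulated data sets were analysed with and without the two scores entered linearly (6,000 replicates per row). Assumptions, none given in the documents: an equal latent correlation r of each score with recovery, a correlation of 0.4 between the scores, and the period split. The joint latent R² is then 2r²/(1 + 0.4).

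| r | R² | SMT power, without → with | SSM power, without → with | Gain in points (SMT / SSM) |
|---|---|---|---|---|
| 0.1 | 0.014 | 77.3 → 77.5% | 85.6 → 85.5% | 0.2 / −0.1 |
| 0.2 | 0.057 | 77.8 → 78.4% | 86.1 → 86.7% | 0.6 / 0.6 |
| 0.3 | 0.129 | 77.3 → 79.7% | 85.8 → 87.7% | 2.4 / 1.9 |
| 0.4 | 0.229 | 77.6 → 82.1% | 86.0 → 89.4% | 4.5 / 3.4 |

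In the 5% and 15% scenarios at r = 0.4 (3,000 replicates) the gain is about 3 to 6 points. At r = 0 there is no gain and no material loss.

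**4. Cross-check in odds ratios.** With one baseline score, and site and risk group in the model (3,000 trials), the gain is 0.1 to 0.3 points at an odds ratio per SD of 1.2, 0.5 to 1.0 at 1.5, and 2 to 3 at 2.2.

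**5. Validity.** Under the null, simulated rejection is 5.4 to 5.8% with or without the two covariates.

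**The case against.** The strongest reply is that nothing here is wrong. Adjusting a secondary binary endpoint for the stratification factors and period is an ordinary, valid choice, and the stated power reproduces. That stands; the point is about efficiency.

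The prognostic strength of the baseline scores is also unknown. Section 4.1 requires NRS of at least 3 and medium or high STarT Back risk, which restricts the range, and the risk-group term may already carry part of baseline severity. That stands too, and it is why the range has to start at zero.

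The comparison with the pain and disability models is not exact. There the baseline is the same variable as the outcome, whereas every participant enters unrecovered. So this is not a contradiction in the plan. The plan's own reason for adjusting, that predictors of outcome improve power, still carries over to these two scores.

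Finally, the exclusion is inferred: the recovery section is silent, and the power text does not say that site and risk are the only adjusters. This is right, and it is itself a reason to write the list down.

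A reader might infer that the omission explains SMT power below 80%, or that strong covariates are being discarded at no cost. The documents support neither. The shortfall comes mainly from period adjustment under an assumed split, no prognostic strength is given, and adding covariates changes what the odds ratio means.

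**Conclusion.** The point holds as a minor one. As far as the plan can be read, recovery is adjusted for site, risk group and period but not for baseline NRS and RMDQ. The cost is somewhere between nothing and about 4.5 points of power in the 10% scenario, and about 3 to 6 points in the 5% and 15% scenarios at the strongest association tried. These sizes rest on an assumed latent correlation of 0 to 0.4, 900 evaluated participants and an assumed period split. Entry restrictions and the risk-group term may hold the gain toward the lower end. Neither bias nor type I error is at issue.

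**What to change.** Before unblinding, write out the logistic models for recovery at 6 and 12 months with their full covariate list: site, risk group, period, the SMT, SSM and interaction terms, and continuous baseline NRS and RMDQ. Keep the two average-effect contrasts as they are.

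Beside each odds ratio, report a covariate-standardised risk difference. For SMT this is ½[(R10 − R00) + (R11 − R01)], where Rab is the mean predicted recovery risk over all analysed participants with SMT set to a and SSM set to b; SSM is analogous. This also matches the recovery hypothesis, which is framed in percentage points.

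The cost is SAP wording and two covariates, with no new data collection. The one downside is that the odds ratio becomes conditional on baseline severity, so it is not directly comparable with one from the smaller model; the standardised risk difference addresses that.

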LBP Impact Effectiveness Hypothesis: SMT alone will decrease the impact of low back pain with at least a moderate effect size of 0.3 standard deviations (Cohen's d). Similarly, SSM alone will decrease the impact of low back pain with at least a moderate effect size of 0.3 standard deviations. The combination SMT+SSM will lead to a stronger but not necessarily additive net reduction compared to the individual component interventions.

Design: As shown in Figure 9.1, we plan to enroll a total of 1000 subjects randomized to one of four treatment groups using a factorial design: medical care (MC); spinal manipulation therapy alone (SMT); supported self-management alone (SSM); and combined SMT+SSM.

LBP Impact Primary Analysis: Our primary analysis will compare each of the treatment groups to MC using an adjusted regression analysis. Specifically, Let Y_{ij} denote the primary outcome variable (average of LBP-Impact over months 10-12) for subject i in site j, and let $Site(2)$ be an indicator variable used to code the two recruitment sites. All analyses will adjust for site and the baseline risk status represented by $RiskGroup$ (0=medium risk; 1=high risk). In order to code the treatment groups we use the variables *SMT-Only* (0=no; 1=only spinal manipulation therapy), *SSM-Only* (0=no; 1=only supported self-management), and *SMT-and-SSM* (0=no, 1=both SMT and SSM). Given interruption by COVID-19 and an associated period of restricted randomization we will also adjust for this modified randomization using the variables *Period(k)* which will be an indicator for: 1=UG3 and UH3 through March 2020; 2=calendar period of restricted randomization; and 3=calendar period of resumed full factorial randomization. We will use an adjusted linear regression model with robust standard error to make inference regarding treatment groups using the following structure where X_{ij} denotes the covariates for subject i:

$$E(Y_{ij} | X_{ij}) = \beta_0 + \beta_1 \cdot Site(2)_j + \beta_2 \cdot RiskGroup_{ij} + \beta_3 \cdot SMT-Only_{ij} + \beta_4 \cdot SSM-Only_{ij} + \beta_5 \cdot SMT-and-SSM_{ij} + \beta_6 \cdot Period(2)_{ij} + \beta_7 \cdot Period(3)_{ij}$$

In the primary regression model the parameters of interest are:

β_3 = adjusted mean difference comparing SMT Only to UMC;

β_4 = adjusted mean difference comparing SSM Only to UMC;

β_5 = adjusted mean difference comparing combined SMT and SSM to UMC.

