Effectiveness Hypothesis: We will focus on parallel analyses for pain and function. We hypothesize that SMT alone will decrease average pain by at least 1 point, and average disability by 2 points. Similarly, SSM alone will decrease average pain by at least 1 point, and average disability by 2 points, and the combination of SMT+SSM will lead to an sub-additive net decrease of <2 points and <4 points respectively.

Primary outcome variables: We will derive measure of disability and pain by calculating the time-averaged patient outcome using the monthly measurements taken over the year of follow-up.

Primary Analysis: For quantitative outcomes we will focus on analyses that generally do not assume that the effects of SMT and SSM are additive since we have adequate power to evaluate specific group contrasts. We will use linear regression methods with robust standard errors to test for the difference in mean scores comparing each intervention group to MC. Let Y_{ij} denote the outcome of interest (either average pain or average disability for parallel analyses). Similar to our primary analysis of LBP impact 1 we will use a linear regression model with robust standard errors using the structure:

$$\text{Four Groups Model: } E(Y_{ij} | X_{ij}) = \beta_0 + \beta_1 \cdot \text{Site}(2)_j + \beta_2 \cdot \text{RiskGroup}_{ij} + \beta_3 \cdot \text{SMT-Only}_{ij} + \beta_4 \cdot \text{SSM-Only}_{ij} + \beta_5 \cdot \text{SMT-and-SSM}_{ij} + \beta_6 \cdot \text{Period}(2)_{ij} + \beta_7 \cdot \text{Period}(3)_{ij}$$

In the primary regression model the parameters of interest are:

β_3 = adjusted mean difference comparing SMT Only to UMC;

β_4 = adjusted mean difference comparing SMT Only to UMC;

β_5 = adjusted mean difference comparing combined SMT and SSM to UMC.

This model considers each treatment group separately using an indicator of SMT only (*SMT-Only*), an indicator of SSM only (*SSM-Only*), and an indicator of combined therapy with both SMT and SSM (*SMT-and-SSM*). We will also add the baseline outcome as a covariate to perform a variation of ANCOVA for repeated measures.

Table 9.2: Power for the overall F-test of equality of means under various alternative scenarios.

Average pain intensity & disability over 12 months post-randomization (alpha = 0.05/2)

Alternative	SMT Alone	SSM Alone	SMT + SSM	Power
Additive	0.20	0.20	0.40	88%
Sub-Additive 1	0.25	0.25	0.35	85%
Sub-Additive 2	0.30	0.30	0.30	89%
Sub-Additive 3	0.25	0.25	0.25	74%

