Power and Sample Size for primary effectiveness outcomes # 2 and # 3: See Table 9.2. We will conduct longitudinal analysis of the underlying RMDQ and Pain NRS scores. Specifically, we will conduct analyses using the mean area under the curve for both disability and pain and use linear regression to evaluate treatment effects on the native underlying scales. With n=1000 subjects evaluated through one year and using alpha=0.05/2 for the two outcomes and an overall F-test we have >80% power across a range of scenarios presented in the table below. To orient standardized effects a marginal 2-point mean difference on RMDQ for any treatment modality compared to UMC assuming a standard deviation of 6.5 or less,^{149 153} corresponds to a Cohen's D of $2.0/6.5 = 0.31$, and >80% power to detect a marginal 1-point difference on Pain NRS assuming a standard deviation of 3.0 or less corresponds to a standardized effect of 0.33.^{149 153} Note that our outcome is the area under the curve through 12 months, which is a patient-level weighted average, and the standard deviation (SD) for this outcome will be less than the SD for a single measurement. Our power calculations are conservative since we use the SD for a single measurement. Although we have <80% power if SMT and SSM have small marginal effects of 0.25 SD and no additional benefit when combined (sub-additive 3 below) this scenario leads to no single treatment arm yielding an effect of 2 points on RMDQ (0.31 SD) or 1 point on Pain NRS (0.33 SD) and therefore suggests our design is appropriate for important and plausible effect sizes and not overpowered for effects that may not be meaningful.

Furthermore, we have excellent power to detect interaction effects where the effect of SMT and SSM may be synergistic or antagonistic, and using alpha=0.05/2 we have >80% to detect a 2.7-point difference in disability or 1.3-point difference in pain treatment effects of one modality across the strata defined by the other treatment modality.

Secondary Analyses of the 3 primary effectiveness outcomes and other secondary outcomes: We will conduct a number of pre-specified secondary analyses.

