Missing data may include missing covariate information, study dropout, or missed and/or mistimed participant visits. While the PACBACK protocol includes procedures to ensure the most “complete” follow-up data on every enrolled participant, it is likely that some participants will have incomplete data. We will determine reasons for missingness, classifying each missingness pattern as missing completely at random (MCAR), missing at random (MAR), or missing not at random (MNAR). The MCAR mechanism occurs when the probability of response is independent of both the observed data and the unobserved data¹⁷⁰. All protocols will include recommended sensitivity analyses that will help determine the extent of potential biases that could affect the results.

In longitudinal analyses, likelihood-based analyses of complete-case data for the linear mixed-effects model, the generalized linear mixed-effects model, and the nonlinear mixed-effects model lead to valid inference under MCAR and MAR mechanisms, whereas the GEE analyses lead to valid inference only in the presence of MCAR mechanisms.^{170 171} Statistical tests to assess the validity of the MCAR assumption in certain circumstances are available, but they are model-dependent and non-robust.¹⁷²⁻¹⁷⁴ In general, we will advocate the use of multiple imputation (MI)¹⁷⁵ both to assess the sensitivity of results and to correct for bias from missing covariates. We will consider the missing data mechanism, analysis approach, and plausibility of the congeniality assumption.^{176 177} If MNAR data are suspected, there are three basic approaches to address this challenge, namely, (1) selection models¹⁷⁸⁻¹⁸⁰, (2) pattern-mixture models^{181 182} and (3) MI.^{175 183} We recommend MI because it appears to be more robust. We can apply MI using weights dependent on the probability of dropout to assess the dependence of results on dropout.

We will also consider selection models with varying dropout parameters in sensitivity analyses.^{183 184}

Potential Problems & Alternative Strategies:

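### The primary regressions use one average per patient, with no rule for incomplete averages and no imputation tied to the primary result

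*Combined protocol and SAP*

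**What the plan says.** All references are to the combined protocol and SAP.

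- **Pain and RMDQ** (Section 9, Primary Effectiveness Outcome # 2 and 3). The outcome is one number per patient, built from the year's monthly scores: "We will derive measure of disability and pain by calculating the time-averaged patient outcome". The model follows: "We will use linear regression methods with robust standard errors to test for the difference in mean scores comparing each intervention group to MC". The baseline value is included: "We will also add the baseline outcome as a covariate". The power paragraph describes the same outcome as an area under the curve: "we will conduct analyses using the mean area under the curve for both disability and pain and use linear regression".
- **LBP Impact** (Section 9, LBP Impact Primary Analysis). The "primary outcome variable (average of LBP-Impact over months 10-12") is analysed in the same form: "We will use an adjusted linear regression model with robust standard error to make inference regarding treatment groups". Its covariates are site, risk group, period and arm. No baseline LBP Impact score is listed.
- **Missing data** (Section 9, General Missing Data Considerations). Likelihood-based longitudinal models are said to be valid under MCAR and MAR. Multiple imputation is favoured in general, "both to assess the sensitivity of results and to correct for bias from missing covariates", and again where MNAR is suspected. None of this is attached to a primary outcome.
- **Longitudinal models** (Section 9). Mixed models or GEE for the pain and disability profiles appear among the secondary analyses.
- **Data collection.** After loss to follow-up the surveys are switched off except at months 6 and 12 (Section 10.3.3). Patients who stop treatment and will not complete full questionnaires may be reduced to months 2, 6 and 12, and the outcomes given as examples for them do not include LBP Impact (Section 8).
- **Design.** Section 3.1 lists an intention-to-treat analysis of all data as a pragmatic feature.

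**The concern.** A per-patient average is well defined only when the months are complete, and the plan itself foresees incomplete records. Different analysts could fill the gap in different ways:

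- **Average whatever months exist.** Acute LBP improves early, so a patient who stops reporting early has a pain or RMDQ average that is too high for the year.
- **Keep only patients with enough months.** If worse patients leave, the arm with more loss looks better than it is.
- **LBP Impact.** Only months 10-12 enter, so a patient with none of them is absent from the analysis, whatever was reported in months 1-9. Without a baseline score in the model, loss related to initial severity is adjusted for only through the two-level risk group.

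The first two choices err in opposite directions, so leaving the choice open until data are seen matters in itself. Loss that differs by arm is plausible: participants are unblinded, attention is deliberately not equalised (Section 3.1), and expected visits run from 2-4 for medical care to 4-8 for SSM (Section 5.4).

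**Working it through.** **Inputs from the documents.** Hypothesised effects are 2 RMDQ points, 1 NRS point and 0.30 SD for LBP Impact. SDs are 6.5 (RMDQ) and 3.0 (NRS). Follow-up is 90% for power (900 of 1000), at least 88% for chronicity, and an 85% target per monthly survey. So planned loss is 10-15%.

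**The plan's own figures.** 2.0/6.5 = 0.31 and 1/3.0 = 0.33 reproduce. For Table 9.2, a noncentral F with 3 df, alpha 0.025 and 270/180/270/180 evaluated (90% of 300/200/300/200) gives 75% for Sub-Additive 3, against a stated 74%. Not every row reproduces (Single effect 2b: 82% computed, 71% stated), and the table does not decide this point.

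**Inputs assumed.** The documents give no trajectories or dropout mechanism. RMDQ is assumed to fall from 11 to 5.5 with a time constant of 1.5 months, and NRS from 5.5 to 3.0. The chance of leaving depends on the last observed score.

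**Step 1: one early leaver.** With m(t) = 5.5 + 5.5·exp(-t/1.5):
- m(1) = 8.32 and m(2) = 6.95, so months 1-2 average 7.64.
- Months 1-12 average 5.98.
- The excess is 7.64 - 5.98 = 1.65 points in that patient's own average.

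**Step 2: from a patient to a contrast.** For available-month averages, contrast bias ≈ (difference in loss between arms) × (excess per leaver). A 10-point difference gives 0.10 × 1.65 = 0.17 RMDQ points if every leaver stops after month 2. It is smaller when some leave later.

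**Step 3: simulation, no true effect.** A positive sign means that the arm with more loss looks worse.

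| Outcome and handling | Loss by arm | Bias |
|---|---|---|
| RMDQ, available months | 20% v 10% | +0.12 points |
| RMDQ, available months, baseline covariate, no later surveys | 20% v 10% | 0.15 (size) |
| Same, half of the month 6 and 12 surveys answered | 20% v 10% | 0.09 (size) |
| Same, all of them answered | 20% v 10% | 0.05 (size) |
| RMDQ, available months, baseline covariate (none / half / all answered) | 15% v 10% | 0.08 / 0.06 / 0.01 (size) |
| RMDQ, available months, baseline covariate | 15% v 15% | about 0 |
| RMDQ, completers only | 20% v 10% | -0.30 points |
| LBP Impact, months 10-12 | about 18-20% v 9-10% | 0.04-0.06 SD (size) |
| All-data estimate valid under MAR | as above | 0.01 or less |

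**Step 4: pain NRS, true effect 1.00 point.**
- Loss 17% (medical care) v 6% (treated): available months 1.06, completers 0.93, likelihood model 1.00.
- Loss about 13% v 9%: 1.01, 0.97 and 0.99.

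**Step 5: against the targets.**
- RMDQ, available months: 0.05/2 to 0.15/2, or 2.5% to 7.5%.
- RMDQ, completers: 0.30/2 = 15%.
- LBP Impact: 0.04/0.30 to 0.06/0.30, or 13% to 20%.

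**Step 6: precision.** If all 1000 patients contributed in full, which is an upper bound for any all-data method, Sub-Additive 3 power at alpha 0.025 would rise from 75% to 81%.

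**The case against.** The strongest reply is that this is a missing rule rather than a demonstrated defect. Much of that stands.

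- **Handling is unspecified.** A reader might infer that early leavers will contribute only their worst months, or that the primary result has no protection at all. The documents say neither. The missing-data section leaves imputation open, including imputation weighted by the probability of dropout, and adds selection-model sensitivity analyses.
- **Later data are still sought.** Months 6 and 12 are pursued after loss to follow-up, and the month 12 window is wide (-14 to +28 days). Month 12 lies inside the LBP Impact window, so one answered survey can keep a leaver in that analysis. This helps only if the survey is answered, and it then supplies one of three months.
- **The early-months mechanism is limited.** It cannot apply to LBP Impact, where leavers are simply absent. Nor is the pain or RMDQ outcome a wholly raw mean: the plan also calls it an area under the curve and adjusts for baseline. Time-weighting shrinks a leaver's excess if months 6 and 12 are present.
- **Individual error is not contrast bias.** It is tempting to set the 1.65-point excess in Step 1 beside the 2-point target. They are different quantities, and the arm contrast moves by about a tenth as much when loss differs by 10 points. It is also tempting to suppose that opposite kinds of patient leave the two arms; nothing in the documents supports that as a planning case.
- **20% v 10% is pessimistic.** It averages 15% with equal arms, the edge of planned loss, and doubles loss between arms.
- **The comparison favours MAR methods.** Loss was simulated as MAR, so near-zero bias for a MAR method is built in.
- **Averages with ANCOVA are legitimate, and mixed models are already planned.** Both are true. But the mixed models are secondary, and the plan credits likelihood models with validity under MAR without placing one where the primary conclusion is drawn.

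**Conclusion.** The concern holds in a limited form. All three primary outcomes are per-patient averages in a one-record regression, with no rule for incomplete averages and no imputation tied to the primary result. LBP Impact is the most exposed: earlier scores are unused, and the model has no baseline score.

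The likely bias is modest: roughly 0.05-0.15 RMDQ points with available months, about 0.3 points in the opposite direction with completers, and 0.04-0.06 SD for LBP Impact. These figures rest on assumed trajectories and on score-dependent loss of about 20% v 10%. They shrink with smaller differences in loss and as month 6 and 12 surveys are answered. With no true effect and equal loss of the same type in both arms, they vanish. This is a worthwhile, inexpensive improvement, not a fatal flaw.

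**What to change.** State one primary method for incomplete records before unblinding. Either would do:

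1. **Visit-level multiple imputation.** Impute missing scores using baseline, all observed scores, arm, site, risk group and Period. Then form the averages and fit the planned regression.
2. **Likelihood mixed model on all observed monthly scores**, with weekly NRS summarised by month and arm-by-time terms. Estimate the year-average contrast for pain and RMDQ and the months 10-12 contrast for LBP Impact.

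In both cases:
- Keep the 3-df Wald test and the stated alphas.
- Bring the baseline score into the LBP Impact analysis.
- Retain the observed-average regression, with its minimum-data rule stated, and MNAR analyses as sensitivity analyses.
- Reconcile the text that builds average pain from monthly measurements with the text that uses weekly NRS.

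**Cost.** A rewritten SAP paragraph and some programming. Data collection, target contrasts and alpha do not change. An imputation or covariance model must be specified; summarising NRS by month avoids a covariance matrix over 52 weekly scores. Neither option cures MNAR loss, so the sensitivity analyses remain necessary.
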